11. DATA COLLECTION AND DATA MANAGEMENT

11.1 Data Collection and Case Report Forms

An electronic data capture system will be used in this trial. A case report form will be completed for each consented patient. The site maintains a separate source of data. This data will be entered by the site into the electronic data capture system.

The investigator is ultimately responsible for the collection and timely reporting of all applicable data entered in CRFs and any other data collection forms (source documents) and ensuring they are accurate, original, attributable, complete, legible, contemporaneous, and available when required. Changes to entries made in CRF and source documents must be dated, initialed and explained (if necessary). Changes should not obscure original entry.

Data reported on the CRF that are derived from source documents should be consistent with the source documents or the discrepancies should be explained.

The CRF must be signed by the investigator or by authorized delegate to attest the data in the CRF is true.

11.2 Dose Escalation Safety Cohort Review

Within 7 working days of each patient completing cycle 1 of Part A dose escalation, the following sections of the eCRF and source documentation for laboratory results must be completed and submitted to the Clinical Trials Specialist/Manager at Ozmosis Research Inc.:

- Study Treatment Administration
- Adverse Effects
- Hematology and Biochemistry Results
- Bone Marrow Results, if performed (optional)
- Lab normal ranges page, if applicable

Additional information may also be requested by Ozmosis Research Inc. from the study site. It is imperative that the eCRF pages listed above are received at Ozmosis Research Inc. within 7 working days after the patient completes cycle 1 and starting cycle 2 day 1 study drug administration, as the information will be used to assess safety at the opened dose level and to determine the feasibility of proceeding to a new dose level.

12. ADMINISTRATIVE, ETHICAL, AND REGULATORY STANDARDS

12.1 Compliance Statement

This trial will be conducted in compliance with the protocol, ICH-GCP's and the applicable regulatory requirement(s).

12.2 Ethics

This trial will be submitted and approved by the local Research Ethics Board prior to patient accrual.

12.3 Regulatory Requirements

The following documents are required:

For participating Canadian centres:

- All Investigators must complete and sign the Health Canada Qualified Investigator Undertaking form. The completed forms must be returned to the sponsor prior to any drug shipment.
- All applicable regulatory documents as listed in the Protocol Activation Checklist provided by Ozmosis Research Inc. to the sites.

- Ozmosis Research Inc. will submit via fax or e-mail to Health Canada a completed Health Canada Clinical Trial Site Information Form after local activation of each participating Canadian centre.

For participating U.S.A. centres:

- All Investigators must complete and sign FDA Form 1572. The completed forms must be returned to the sponsor prior to site activation.
- All Investigators must complete and submit a Financial Disclosure Statement.
- All Investigators must also submit to Ozmosis Research Inc. an up-to-date (current to within 2 years of the study start) curriculum vitae.
- Laboratory certification / accreditation and normal ranges for local lab(s).
- Consent forms, reviewed by Ozmosis Research Inc. before submission to the local Institutional Review Board (IRB).
- A completed site delegation list.
- A copy of the initial full board approval letter from the local IRB. Continuing approval (full board) will be obtained at least yearly until follow-up on patients is completed and no further data is being obtained for research purpose.

12.4 Confidentiality and Data Protection

12.4.1 Participant Protection

The responsible investigator will ensure that this study is conducted in compliance with the protocol and in agreement with the Declaration of Helsinki.

The protocol has been written, and the study will be conducted according to the ICH Harmonized Tripartite Guideline on Good Clinical Practice.

The local research ethics board must approve the protocol, Informed Consent Form and any trial materials given to participants.

All potential serious breaches of GCP must be reported to Sponsor or designee immediately. A serious breach is a breach of the conditions and principles of GCP in connection with the study or the protocol, which is likely to affect, to a significant degree, the safety or physical or mental integrity of the participants of the study or the scientific value of the study.

12.4.2 Participant Identification

A sequential identification number will be automatically allocated to each patient registered in the trial. This number will identify the patient and will be included on all CRFs.

12.4.3 Confidentiality of Trial Documents and Patient Records

The investigators must assure that participants' anonymity will be maintained and that their identities are protected from unauthorized parties. On CRFs patients should not be identified by their names, but by an identification code. Investigators should keep patients' written consent forms and a patient enrolment log at the site showing codes, names and addresses.

12.4.4 Retention of Patient Records and Study Files

The investigator must retain all study records and source documents for the maximum period required by applicable regulations and guidelines, or institution procedures, whichever is longer.

12.5 Protocol Registration

The sponsor has committed to the global industry position on disclosure of information about clinical trials. The International Committee of Medical Journal Editors (ICMJE) also requires trial registration as a condition of the publication of research results generated by a clinical trial. The

information regarding this trial will be made publicly available on the internet at www.clinicaltrials.gov.

12.6 Protocol Amendments

Before study initiation, the Sponsor (or designee) must have written and dated approval/favorable opinion from the REB/IRB/Independent Ethics Committee (IEC) and Health Canada (HC) (if applicable) for the protocol, consent form, subject recruitment materials (e.g., advertisements), and any other written information to be provided to participants. The Sponsor should also provide the REB/IRB/IEC and HC (if applicable) with a copy of the Investigator Brochure, Product Monograph, etc. (as applicable).

The Sponsor or designee should provide the REB/IRB/IEC and HC (if applicable) with reports, updates and other information (e.g., expedited safety reports, amendments, and administrative letters) according to regulatory requirements or institution procedures.

13. CRITERIA FOR TERMINATION OF TRIAL

The Sponsor (or designee) has the right to close this study (or, if applicable individual segments thereof at any time, which may be due but not limited to the following reasons:

13.1 Futility

If the study conduct (e.g. recruitment rate, drop-out rate, data quality, protocol compliance) does not suggest a proper completion of the study within a reasonable time frame the Sponsor may consider terminating the trial. This will be done in consultation with the DSMB.

13.2 Safety

If risk-benefit ratio becomes unacceptable owing to, for example,

- Safety findings from this study (e.g. SAEs);
- Results of any interim analysis
- Results of parallel clinical studies
- Results of parallel animal studies (e.g. toxicity, teratogenicity, carcinogenicity or reproduction toxicity).

13.3 Efficacy

For any of the above closures, the following applies:

- Closures should occur only after consultation between involved parties.
- All affected institutions (e.g. REB; competent authorities; study centre(s)) must be informed as applicable according to local law.
- All study materials (except documentation that has to remain stored at site) must be returned to the sponsor. The investigator will retain all other documents until notification given by the sponsor for destruction.
- In case of a partial study closure, ongoing participants, including those in post study follow-up, must be taken care of in an ethical manner

14. PUBLICATION POLICY

The results of this study may be published or presented at scientific meetings. If this is foreseen, the Principal Investigator agrees to submit all manuscripts or abstracts to the Sponsor for approval prior to submission. Authors of the manuscript and abstracts will include at least the Principal

Investigator (as first author) and co-investigators who have i) included eligible patients in the trial (by order of inclusion) or ii) contributed significantly to the design, conduct and data interpretation regarding companion basic science studies.

The data collected during this study are confidential.

16. LIST OF APPENDICES

Appendix A. Eastern Cooperative Oncology Group Scale for Performance Status Grade Description

0	Normal activity. Fully active, able to carry on all pre-disease performance without restriction.
1	Symptoms but ambulatory. Restricted in physically strenuous activity, but ambulatory and able to carry out work of a light or sedentary nature (eg, light housework, office work).
2	In bed <50% of the time. Ambulatory and capable of all self-care, but unable to carry out any work activities. Up and about more than 50% of waking hours.
3	In bed >50% of the time. Capable of only limited self-care, confined to bed or chair more than 50% of waking hours.
4	100% bedridden. Completely disabled. Cannot carry on any self-care. Totally confined to bed or chair.
5	Dead

Source: Oken MM, Creech RH, Tormey DC, Horton J, Davis TE, McFadden ET, et al. Toxicity and response criteria of the Eastern Cooperative Oncology Group. American Journal of Clinical Oncology 1982;5(6):649-55.

Appendix B. Response Evaluation Criteria In Solid Tumors (RECIST Version 1.1)

The following information is extracted/summarized from Eisenhauer, 2009, New Response Evaluation Criteria in Solid Tumors: Revised RECIST Guideline (Version 1.1). Please refer to the primary reference for further information.

Definitions

At screening, tumor lesions/lymph nodes will be categorized as measurable or non-measurable.

Measurable Disease

Tumor Lesions. Must be accurately measured in at least one dimension (longest diameter in the plane of measurement is to be recorded) with a minimum size of:

- 10 mm by CT scan (CT scan slice thickness no greater than 5 mm)
- 10 mm caliper measurement by clinical exam (lesions which cannot be accurately measured with calipers should be recorded as non-measurable)
- 20 mm by chest X-ray

Malignant Lymph Nodes. To be considered pathologically enlarged and measurable, a lymph node must be ≥ 15 mm in short axis when assessed by CT scan (CT scan slice thickness recommended to be no greater than 5 mm). At baseline and in follow-up, only the short axis will be measured and followed.

Non-measurable Disease

All other lesions, including small lesions (longest diameter <10 mm or pathological lymph nodes with ≥ 10 to < 15 mm short axis) as well as truly non-measurable lesions. Lesions considered truly non-measurable include: leptomeningeal disease, ascites, pleural or pericardial effusion, inflammatory breast disease, lymphangitic involvement of skin or lung, abdominal masses/abdominal organomegaly identified by physical exam that is not measurable by reproducible imaging techniques.

Choosing Target Lesions

- Select up to 5 lesions (up to 2 per organ).
- Select largest reproducibly measurable lesions.
- If the largest lesion cannot be measured reproducibly, select the next largest lesion which can be.
- Add up longest diameters (LD) of non-nodal lesions (axial plane).
- Add short axis diameters of nodes.
- This is the sum of the longest diameters (SLD).

Nontarget Lesions

- All other sites of disease present at baseline and not classified as target lesions will be classified as nontarget lesions, including any measurable lesions that were not chosen as target lesions.
- It is possible to record multiple nontarget lesions involving the same organ as a single item on the eCRF (eg, “multiple enlarged pelvic lymph nodes”).
- Measurements are not required but these lesions should be noted at baseline and should be followed as “present,” “absent,” or “unequivocal progression.”

Determining Response

- Assess at baseline and on study with consistent modalities (CT, MRI, PET/CT).
 - Measure target lesions and calculate SLD.
 - Visually assess nontarget lesions.
 - Search for new lesions.
 - Combine these assessments into the overall response.

Target Lesion Response

Complete response (CR)	
• Disappearance of all extranodal target lesions.• All pathological lymph nodes must have decreased to <10 mm in short axis.
Partial response (PR)	
• At least a 30% decrease in the SLD of target lesions, taking as reference the baseline sum diameters.
Progressive disease (PD)	
• SLD increased by at least 20% from the smallest value on study (including baseline, if that is the smallest).• SLD must also demonstrate an absolute increase of at least 5 mm. (2 lesions increasing from, for example, 2 mm to 3 mm, does not qualify).
Stable disease (SD)	
• Neither sufficient shrinkage to qualify for PR nor sufficient increase to qualify for PD.
Nonevaluable (NE)	
• One or more lesions cannot be evaluated because of missing data or poor image quality unless a convincing argument can be made that the contribution of the individual missing lesion(s) would not change the assigned time point response (eg, PD based on other findings).

Abbreviations: SLD, sum of the longest diameters.

Nontarget Lesion Response

Complete response (CR)	
• Disappearance of all extranodal nontarget lesions.• All lymph nodes must be nonpathological in size (<10 mm short axis).• Normalization of tumor marker level.
Non-CR/non-PD	
• Persistence of 1 or more nontarget lesions(s) and/or maintenance of tumor marker level above the normal limits.
Progressive disease (PD)	
• Unequivocal progression of existing nontarget lesions (subjective judgment by experienced reader).
Unable to evaluate (UE)	
• One or more lesions cannot be evaluated because of missing data or poor image quality unless a convincing argument can be made that the contribution of the individual missing lesion(s) would not change the assigned time point response (eg, PD based on other findings).

New Lesions

- Should be unequivocal and not attributable to differences in scanning technique or findings which may not be a tumor (does not have to meet criteria to be "measurable").
- If a new lesion is equivocal, continue to next time point. If confirmed then, PD is assessed at the date when the lesion was first seen.
- Lesions identified in anatomic locations not scanned at baseline are considered new.
- New lesions on ultrasound should be confirmed on CT or MRI.

Evaluation of Overall Time Point Response for Patients With Measurable Disease at Baseline

Abbreviations: CR, complete response; PR, partial response; PD, progressive disease; SD, stable

Target Lesions	Nontarget Lesions	New Lesions	Overall Response
CR	CR	No	CR
CR	Non-CR/non-PD	No	PR
CR	NE	No	PR
PR	Non-PD or NE	No	PR
SD	Non-PD or NE	No	SD
Not all evaluated	Non-PD	No	NE
PD	Any	Yes or no	PD
Any	PD	Yes or no	PD
Any	Any	Yes	PD

disease; NE, nonevaluable.

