23. Radiotherapy to target lesions in the 21 days before starting the first dose of study drug. Palliative radiotherapy is allowed to non-target lesions at any time before starting the first dose of study drug.
24. Major surgery or significant trauma within 4 weeks before the first dose of study drug
25. Previous assignment to treatment during this study
26. Concomitant participation in another clinical study with investigational medicinal product(s)
27. Substance abuse, medical, psychological, or social conditions that may interfere with the patient's participation in the study or evaluation of the study results
28. Close affiliation with the investigational site; e.g. a close relative of the investigator, dependent person (e.g. employee or student of the investigational site)
29. Use of strong CYP3A4 inhibitors and inducers from 14 days prior to first administration of study drug. Strong CYP3A4 inhibitors and inducers are prohibited during the study and until the active FU visit.
30. Use of Proton Pump Inhibitors (PPIs) must be discontinued at least 48 hours prior to initiation of study drug.

Note: If a potential participant is on a PPI and requires some form of Acid Reducing Agent(s) (ARAs), the investigator should consider alternatives for the duration of the trial, including Famotidine, or oral antacid drugs such as calcium carbonate.

31. Clinically relevant findings in the ECG such as a second- or third-degree atrioventricular block, prolongation of the QRS complex > 120 ms (except for bundle branch block pattern), or prolongation of the QTc interval (Fridericia) over 450 ms unless agreed otherwise between the investigator and the sponsor's medically responsible person.

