6. NON-STUDY THERAPIES

6.1 Concomitant Therapy

Concomitant therapy includes any prescription medications or over-the-counter preparations used by a participant between the 7 days preceding the baseline evaluations and the end of last study visit. All concomitant medications (including start / stop dates, total daily dose, and indication), including vaccinations, should be reported by the Investigator and recorded on the appropriate eCRF.

Permitted Therapies

- Patients may receive palliative and supportive care for any underlying illness.
- Patients may receive vaccinations for COVID-19. Ideally, vaccinations would not be administered during Cycle 1 of study treatment, however, this is not prohibited.
- Corticosteroids use for cytoreduction due to malignancy-related symptom control of B-cell lymphoma may be given prior to initiation of study treatment (up to 100 mg/day of prednisone or equivalent for no more than 5 days).
- Palliative radiotherapy during the study will be allowed for local pain control if:

- In the opinion of the investigator, the patient does not have progressive disease.
- Not more than 10% of the patient's bone marrow is irradiated.
- The radiation field does not encompass a target lesion; the indication for radiation therapy to a target lesion is considered progressive disease.
- The safety of oral PCLX-001 administered concomitantly to radiation therapy has not been determined. Therefore, oral PCLX-001 treatment should be held on those days where the patient receives palliative radiotherapy, and restarted the day after completion of palliative radiotherapy.
- Patients may continue receiving bisphosphonates prophylactically or for bone metastases while on study treatment.
- Granulocyte colony-stimulating factor and other hematopoietic growth factors may be used for the management of acute toxicity, such as febrile neutropenia, when clinically indicated or at the investigator's discretion, except their preventive use in Cycle 1.
- CYP3A4 substrates should be used with caution, as exposure may be higher or lower when concomitantly administered with PCLX-001 due to CYP3A4 inhibition or induction, respectively.
- P-gp substrates (e.g. aliskiren, ambrisentan, colchicine, dabigatran etexilate, digoxin, fexofenadine, maraviroc, posaconazole, ranolazine, saxagliptin, sitagliptin, talinolol, tolvaptan) should be used with caution.

Prohibited Therapies

- Use of PPIs must be discontinued at least 48 hours prior to initiation of study drug.

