Extranodal lesions	New FDG-avid foci consistent with lymphoma at interim or end-of-treatment assessment	An individual node/lesion must be abnormal with: LDi > 1.5 cm and Increase by \geq 50% from PPD nadir and An increase in LDi or SDi from nadir 0.5 cm for lesions \leq 2 cm 1.0 cm for lesions $>$ 2 cm In the setting of splenomegaly, the splenic length must increase by $>$ 50% of the extent of its prior increase beyond baseline (eg, a 15-cm spleen must increase to $>$ 16 cm). If no prior splenomegaly, must increase by at least 2 cm from baseline New or recurrent splenomegaly
Nonmeasured lesions	None	New or clear progression of preexisting nonmeasured lesions

New lesions	New FDG-avid foci consistent with lymphoma rather than another etiology (eg, infection, inflammation). If uncertain regarding etiology of new lesions, biopsy or interval scan may be considered	Regrowth of previously resolved lesions A new node > 1.5 cm in any axis A new extranodal site > 1.0 cm in any axis; if < 1.0 cm in any axis, its presence must be unequivocal and must be attributable to lymphoma Assessable disease of any size unequivocally attributable to lymphoma
Bone marrow	New or recurrent FDG-avid foci	New or recurrent involvement

5PS = 5-point scale; CT = computed tomography; FDG = fluorodeoxyglucose; GI = gastrointestinal; IHC = immunohistochemistry; LDi = longest transverse diameter of a lesion; MRI = magnetic resonance imaging; PET = positron emission tomography; PPD = cross product of the LDi and perpendicular diameter; SDi = shortest axis perpendicular to the LDi; SPD = sum of the product of the perpendicular diameters for multiple lesions.

* A score of 3 in many Subjects indicates a good prognosis with standard treatment, especially if at the time of an interim scan. However, in trials involving PET where escalation is investigated, it may be preferable to consider a score of 3 as inadequate response (to avoid undertreatment).

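### Non-target lesions irradiated on study are still scored for response, so radiotherapy can turn a PR into a CR and may mask non-target progression

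*Combined protocol and SAP*

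**What the plan says.** Section 6.1, under permitted therapies: "Palliative radiotherapy during the study will be allowed for local pain control if" three conditions are met. The first is a judgement: "In the opinion of the investigator, the patient does not have progressive disease". The second limits the share of marrow irradiated. The third is "The radiation field does not encompass a target lesion; the indication for radiation therapy to a target lesion is considered progressive disease". Nothing restricts irradiation of a non-target lesion or attaches a response consequence to it. Exclusion criterion 23 in Section 4.2 adds: "Palliative radiotherapy is allowed to non-target lesions at any time before starting the first dose of study drug".

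Appendix B makes every baseline site that is not a target lesion a non-target lesion, with no exception for irradiated sites. Non-target CR needs "Disappearance of all extranodal nontarget lesions", nodes of non-pathological size and normal tumour markers. Unequivocal growth of a non-target lesion is overall PD. A non-target lesion is unevaluable only for missing data or a poor image. In Appendix C, CT-based CR needs nonmeasured lesions to be absent, and CT-based PD includes "New or clear progression of preexisting nonmeasured lesions".

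Section 7.3 sends the investigator to these appendices. The efficacy population (Table 8-1) and Section 8.4 contain no rule for assessments after radiotherapy.

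**The concern.** The secondary objective is the single-agent activity of PCLX-001, the expansion cohorts exist to estimate it, and Section 3.5 makes ORR one input to the RP2D. Radiotherapy is a second, local anticancer treatment. If the lesion it treats is scored as any other, its effect is credited to the drug. Both possible errors, a CR that should be a PR and a progression that is not seen, favour the drug.

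There is a related loose end. Section 6.1 says that "the indication for radiation therapy to a target lesion is considered progressive disease". The PD definitions in Appendices B and C do not list this; for target lesions Appendix B asks for "SLD increased by at least 20% from the smallest value on study" and an absolute increase of at least 5 mm. A patient with a painful target lesion that has not grown that much could be recorded as PD under one section and SD under the other. Disease progression is a reason to discontinue PCLX-001 in Section 3.6, so the category matters beyond the response table.

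**Working it through.** The plan states no figure to reproduce here. The check applies the overall-response table of Appendix B, which covers patients with measurable disease, and asks what changes if radiotherapy improves the non-target category. No new lesions are assumed.

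| Target | Non-target without radiotherapy effect | Non-target as read | Overall without effect | Overall as read | Response at that time point |
|---|---|---|---|---|---|
| CR | Non-CR/non-PD | CR | PR | CR | yes in both |
| PR | Non-CR/non-PD | CR | PR | PR | yes in both |
| SD | Non-CR/non-PD | CR | SD | SD | no in both |
| CR | PD | Non-CR/non-PD | PD | PR | no becomes yes |
| CR | PD | CR | PD | CR | no becomes yes |
| PR | PD | Non-CR/non-PD or CR | PD | PR | no becomes yes |
| SD | PD | Non-CR/non-PD or CR | PD | SD | no in both |
| PD | any | any | PD | PD | no in both |

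**Route 1, false CR (rows 1 to 3).** Only row 1 changes. It needs all target lesions in CR, all other non-target disease gone and normal markers. The CR rate rises; ORR does not.

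**Route 2, masked progression (rows 4 to 7).** A non-target lesion that would have progressed unequivocally is held back. With target CR or PR, the time point becomes a response; with target SD, PD becomes SD. ORR rises only if no PR or CR had been recorded earlier, because an earlier response would already count as best response. The target lesions must also have shrunk by at least 30% while a non-target lesion would have grown, in a patient judged not progressive when irradiated.

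**Lymphoma.** The CT-based criteria of Appendix C have the same structure: nonmeasured lesions must be absent for CR, may have merely regressed for PR, and their clear progression is PD.

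**Size.** One patient in a cohort of 20 is 1/20 = 5 percentage points. With illustrative counts and exact (Clopper-Pearson) 95% intervals:
- 2/20 = 10% (1.2% to 31.7%)
- 3/20 = 15% (3.2% to 37.9%)

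The number of patients irradiated is not in the documents. If 5% to 15% of a cohort were irradiated (an assumption), that is 0.05 × 20 = 1 to 0.15 × 20 = 3 patients. This is a ceiling on the number affected, since it counts everyone irradiated and not only those who also meet the conditions above.

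**The case against.** The strongest reply is that Section 6.1 already protects the endpoint: the patient must not be progressing, and target lesions are kept out of the field. That reduces the problem. But both conditions apply when radiotherapy is given. The first is an opinion with no scan required, while scheduled scans come at the end of every second cycle. Neither says how the irradiated lesion is read afterwards.

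A second reply is that Appendix B is a summary and refers to the primary reference. That source is not part of the documents, so I do not assume that it closes the gap. The protocol wrote its own rule for target lesions and none for non-target lesions.

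Third, response is a secondary, preliminary endpoint without a threshold or test, ORR is one of several RP2D inputs, and no progression-time or response-duration endpoint is defined. This stands and limits the weight of the point.

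Four stronger readings are tempting, and the documents do not support them:
- *Radiotherapy generally inflates ORR.* In measurable disease the false-CR route leaves ORR unchanged; only masked progression can raise it.
- *A patient with non-target disease only becomes a responder.* Such patients are eligible if their disease is evaluable, but the overall-response table covers measurable disease only. No rule in the documents turns their non-target CR into an overall response.
- *Section 6.1 flatly contradicts Appendix B on target lesions.* Section 6.1 can be read as adding a criterion, and nothing in Appendix B denies it. What is missing is one agreed statement.
- *Scoring the irradiated lesion not evaluable from then on would solve it.* That does not recover masked progression: PR or SD with a non-evaluable non-target lesion stays PR or SD. It would also stop later growth of that lesion from counting as PD, and the response table in Appendix C has no such category.

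**Conclusion.** The concern holds in limited form. Followed literally, the scoring rules credit radiotherapy-induced disappearance of a non-target lesion towards CR. In measurable disease this moves PR to CR, under joint conditions, and leaves ORR as it was. Masking of non-target progression is a second route, probably rarer; it can raise ORR or move PD to SD. Each affected patient is 5 points in a cohort of 20 if all 20 are in the efficacy population. How many would be affected cannot be derived from the documents. One such patient is small beside the interval for a rate from 20 patients, about 30 points wide at 2/20 (31.7 − 1.2 = 30.5).

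This is worth correcting because the text gives a definite wrong reading and the remedy is cheap. It affects no sample size or error rate. The treatment of target-lesion radiotherapy in Section 6.1 and in the appendices must be reconciled; this review does not choose the rule.

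**What to change.** 1. Add to Appendices B and C: *A non-target (nonmeasured) lesion irradiated on study cannot contribute to an upgrade to CR; absent other reasons, the time point is at best PR. Unequivocal progression of that lesion, and any new lesion, still counts as PD.* The sponsor should also state whether this covers a lesion irradiated between the baseline scan and the first dose, which Section 4.2 permits.
2. Record lesion site and date of radiotherapy on the eCRF. Section 6.1 describes concomitant therapy as medicines, and Table 7B has no radiotherapy item.
3. List irradiated patients with their response before and after radiotherapy.
4. Report best response and ORR twice: with all assessments, and with only those before radiotherapy. The wording in item 1 cannot recover masked progression, but a response first seen after radiotherapy will show as a difference between the two rates.
5. Reconcile Section 6.1 with the PD definitions in both appendices on target-lesion radiotherapy, so that one patient has one response category.

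The cost is wording in two appendices, an eCRF entry, a listing and a second summary. An occasional true CR in an irradiated patient will be reported as PR, and the analysis before radiotherapy will drop some later true responses. Who may be irradiated or treated does not change.
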